14.1.3 Smoking History

Table 14.1.3.1	Summary of Smoking History at Baseline	Safety Set
Table 14.1.3.2	Summary of Number of Cigarettes Smoked at Baseline	Safety Set

14.2 Efficacy Data

Not Applicable.

14.3 Safety Data

14.3.1 Adverse Events

Table 14.3.1.1	Summary of Treatment Emergent Adverse Events	Safety Set
Table 14.3.1.2	Summary of Treatment Emergent Adverse Events by System Organ Class and Preferred Term	Safety Set
Table 14.3.1.3	Summary of Treatment Emergent Adverse Events by Preferred Term	Safety Set
Table 14.3.1.4	Summary of Treatment Emergent Adverse Events by System Organ Class, Preferred Term and Severity	Safety Set
Table 14.3.1.5	Summary of Treatment Emergent Adverse Events by System Organ Class, Preferred Term and Relationship	Safety Set
Table 14.3.1.6	Serious Adverse Events	Safety Set
Table 14.3.1.7	Adverse Events Leading to Withdrawal of Study Drug	Safety Set

14.3.2 Laboratory Safety

Table 14.3.2.1	Biochemistry Out of Range Data	Safety Set
Table 14.3.2.2	Haematology Out of Range Data	Safety Set
Table 14.3.2.3	Urinalysis Out of Range Data	Safety Set
Table 14.3.2.4	Summary of Absolute and Change from Baseline Biochemistry Data	Safety Set
Table 14.3.2.5	Summary of Absolute and Change from Baseline Haematology Data	Safety Set

14.3.3 Vital Signs

Table 14.3.3.1	Summary of Absolute and Change from Baseline Vital Signs Data	Safety Set
----------------	---	------------

14.3.4 ECG

Table 14.3.4.1	Summary of Absolute and Change from Baseline 12-lead ECG Data	Safety Set
Table 14.3.4.2	Summary of Absolute and Change from Baseline Holter ECG Data	ECG Set
Table 14.3.4.3	Summary of Holter ECG QTcF Categories	ECG Set
Table 14.3.4.4	Summary of Holter ECG Outliers	ECG Set
Figure 14.3.4.1	Mean Change from Baseline Holter ECG Data	ECG Set
Figure 14.3.4.2	Individual Change from Baseline Holter ECG QTcF versus Plasma Cytisine Concentration Data	ECG-PK Set

14.4 Pharmacokinetics

14.4.1 Concentration-Time Data

Table 14.4.1.1	Summary of Plasma Cytisine Concentration Data	PK Set
Table 14.4.1.2	Summary of Plasma Cytisine Concentration Data	Safety Set
Table 14.4.1.3	Summary of Urine Cytisine Concentration Data	PK Set
Table 14.4.1.4	Summary of Urine Cytisine Concentration Data	Safety Set
Figure 14.4.1.1	Mean Plasma Cytisine Concentration-Time Curves - Linear Scale	PK Set
Figure 14.4.1.2	Mean Plasma Cytisine Concentration-Time Curves - Linear Scale	Safety Set
Figure 14.4.1.3	Mean Plasma Cytisine Concentration-Time Curves - Semi-Logarithmic Scale	PK Set

Figure 14.4.1.4	Mean Plasma Cytisine Concentration-Time Curves - Semi-Logarithmic Scale– Non-Elderly Subjects	Safety Set
-----------------	---	------------

14.4.2 Derived Pharmacokinetic Data

Table 14.4.2.1	Summary of Derived Cytisine Pharmacokinetic Parameters	PK Set
Table 14.4.2.2	Summary of Derived Cytisine Pharmacokinetic Parameters	Safety Set
Table 14.4.2.3	Summary of Statistical Analysis of Cytisine C_{max} and C_{min} – Dose Schedule Comparison	PK Set
Table 14.4.2.4	Summary of Statistical Analysis of Cytisine C_{max} and C_{min} – Dose Schedule Comparison	Safety Set
Table 14.4.2.5	Summary of Statistical Analysis of Day 25 Cytisine C_{max} and AUC – Dose Group Comparison	PK Set
Table 14.4.2.6	Summary of Statistical Analysis of Day 25 Cytisine C_{max} and AUC – Dose Group Comparison	Safety Set

14.5 Pharmacodynamics

14.5.1 Pharmacodynamic Data

Table 14.5.1.1	Summary of Absolute and Change from Baseline Daily Cigarette Consumption	PD Set
Table 14.5.1.2	Summary of Smoking Cessation Status	PD Set
Table 14.5.1.3	Summary of Absolute and Change from Baseline Daily Cigarette Consumption by Smoking Cessation Status	PD Set
Table 14.5.1.4	Summary of First Day of Smoking Cessation for Subjects Who Ceased Smoking by Day 26	PD Set
Table 14.5.1.5	Summary of Absolute and Change from Baseline Expired Air Carbon Monoxide (CO) Data	PD Set
Table 14.5.1.6	Summary of Absolute and Change from Baseline Expired Air Carbon Monoxide (CO) by Smoking Cessation Status	PD Set
Table 14.5.1.7	Summary of Absolute and Change from Baseline Urine Cotinine Data	PD Set
Table 14.5.1.8	Summary of Absolute and Change from Baseline Tobacco Craving Questionnaire – Short Form Scores	PD Set
Figure 14.5.1.1	Mean Daily Cigarette Consumption	PD Set
Figure 14.5.1.2	Mean Change from Baseline Daily Cigarette Consumption	PD Set
Figure 14.5.1.3	Mean Daily Cigarette Consumption by Smoking Cessation Status	PD Set

Figure 14.5.1.4	Mean Change from Baseline Daily Cigarette Consumption by PD Set Smoking Cessation Status	
Figure 14.5.1.5	Mean Expired Air Carbon Monoxide (CO) Data	PD Set
Figure 14.5.1.6	Mean Change from Baseline Expired Air Carbon Monoxide (CO) Data	PD Set
Figure 14.5.1.7	Mean Expired Air Carbon Monoxide (CO) by Smoking PD Set Cessation Status	
Figure 14.5.1.8	Mean Change from Baseline Expired Air Carbon Monoxide (CO) by Smoking Cessation Status	
Figure 14.5.1.9	Mean Urine Cotinine Data	PD Set
Figure 14.5.1.10	Mean Change from Baseline Urine Cotinine Data	PD Set
Figure 14.5.1.11	Mean Tobacco Craving Questionnaire – Short Form Total Score	PD Set
Figure 14.5.1.12	Mean Change from Baseline Tobacco Craving Questionnaire – Short Form Total Score	PD Set

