3.5 SAMPLE SIZE CONSIDERATIONS

A total of approximately 36 subjects will be randomised to the study, with approximately 18 subjects per treatment arm (12 aged 18-65 and 6 aged >65).

No previous pharmacokinetic studies with cytisine have reported the effects of repeated administration, so no estimates of intra-subject variability of C_{max} , C_{min} or AUC are available. No specific hypothesis testing is planned. Post-hoc analyses may be performed for PK or PD effects that may appear significantly different between the dosage groups or age groups. In general, the sample size of 36 should be sufficient to meet the exploratory objectives of the study.

Subjects who withdraw from study at any time after randomisation will not be automatically replaced. Replacement based on the number and reason of withdrawals will be at discretion of the Sponsor, following discussion with the Principal Investigator.

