3.6 RANDOMISATION

Subjects will be allocated to Group A (1.5 mg) or Group B (3.0 mg) in accordance with a randomisation code produced by ██████ using the PROC PLAN procedure of SAS® version 9.3. Subjects will be numbered sequentially from 001 (i.e. 001, 002 etc.). Any replacement subjects will be assigned the same randomisation as the subjects they are replacing with 100 added to the subject number (i.e. 101 would replace 001 etc.). Subjects will be stratified for age (elderly > 65 years: yes vs no) to ensure that each dose group has 6 elderly subjects and 12 non-elderly subjects.

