10 STATISTICAL METHODS

10.1 GENERAL PRINCIPLES

- All statistical methods will be based on the International Conference on Harmonisation (ICH) E9 document “Statistical Principles for Clinical Trials”.
- All data collected will be presented within data listings and any unscheduled visits will be listed.
- Data will be summarised by dose group (1.5 mg Cytisine, 3.0 mg Cytisine), age group (18-65 yrs, > 65 yrs, all ages) and overall (both dose groups pooled) where appropriate. The format of the summaries is defined in the shells at the end of this document.
- In summary and analysis tables of continuous variables, standard descriptive statistics (N [number within analysis set, or cohort, or subgroup], n [number of observations included in analysis], mean, standard deviation [SD], median, minimum and maximum) will be presented. Least squares mean (LS mean) and 90/95% confidence interval (CI) will be presented in the statistical analysis outputs as appropriate. For PK summaries, geometric mean, and coefficient of variation (%CV) will also be used to summarise the data.
- Unless otherwise specified, the minimum and maximum statistics will be presented in summary tables to the same number of decimal places as the original data. The mean, median, LS mean, geometric mean and CI will be presented to one more decimal place than the original data. SD will be presented to two more decimal places than the original data. %CV will be presented to one decimal place.
- In summary tables of categorical variables, the number of non-missing observations by category will be presented along with percentages. Unless otherwise specified, the denominator for each percentage will be the number of non-missing observations. All percentages will be presented to one decimal place.
- All plots will use a linear time scale for the nominal times of the visits and will be labelled by time point.
- Original values will be used in summary tables, unscheduled measurements will be listed only. However, where repeats of baseline values occur, unless specified otherwise (i.e. 12-lead ECG), the last assessment will be used within any summary tables and used to calculate change from baseline. In case an unscheduled measurement is performed immediately after the scheduled

measurement due to an error in the original measurement, unless specified otherwise (i.e. 12-lead ECG) the unscheduled measurement will be included in the analysis and the original erroneous measurement will be excluded.

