- The date format for all output presentations will be as captured in the database.
- All statistical analysis will be performed using SAS 9.3 or higher.
- All hypothesis testing will be carried out at the 5% (2-sided) significance level unless stated otherwise.
- P-values will be rounded to four decimal places. P-values less than 0.0001 will be reported as <0.0001 in tables.
- Generally, character values will be left aligned and numeric values will be decimally aligned.
- If any of the assumptions underlying the formal statistical methods proposed are violated during the analysis of the final data, alternative statistical methods will be used and any changes documented in the statistical methods section of the clinical study report (CSR), including the rationale for use.
- For numeric data which includes non-numeric values (e.g. PK data reported as BLQ or laboratory results reported as < 10 or >100) the following principles will be applied when summarising the data:
 - BLQ will be replaced with a zero.
 - Results reported as <x or >x will be treated as x.

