11.5 PD ANALYSES

11.5.1 Number of Cigarettes Smoked and Expired CO

The number of cigarettes smoked in the past 24 hours will be recorded at Screening and daily from Day -1 to Post-Study. Expired air carbon monoxide (CO) data will be obtained at Screening and prior to discharge on days 4, 13, 17, 21 and 26.

The number of cigarettes smoked during the past 24 hours will be taken from the values recorded in the CRF (at CPU) for Screening and Day -1 to Day 3 and from the subject diaries thereafter. In order to evaluate any reduction in smoking, the number of cigarettes smoked daily will be assessed as well as smoking cessation status at Day 26. For each individual subject a smoking cessation status of 'Ceased smoking' will be defined as not having smoked any cigarettes for the past 24 hours on Day 26 and confirmed by an expired CO level <10ppm on Day 26. If these criteria are not satisfied, a smoking cessation status of 'Continued smoking' will be assigned to a subject, including subjects who have missing data at Day 26 for either the number of cigarettes smoked or expired CO level, or both.

The number of cigarettes smoked daily and smoking cessation status will be listed. Frequencies (n, %) of smoking cessation status at Day 26 will be calculated by dose group and age group. For those subjects who had ceased smoking by Day 26, frequencies of the day of first smoking cessation (defined as smoking 0 cigarettes and where cessation is sustained without relapse) will be presented by dose group and age group. Descriptive statistics (N, n, mean, SD, minimum, median and maximum) of absolute and change from baseline (Day -1) number of cigarettes smoked will be tabulated by dose group and age group. The mean absolute values and mean change from baseline will also be presented graphically. Individual subject plots of the number of cigarettes smoked daily will also be produced.

Expired CO levels will be included in the listing that presents the smoking cessation status data. Descriptive statistics (N, n, mean, SD, minimum, median and maximum) of absolute and change from baseline (Screening) expired CO results will be tabulated by dose group and age group. The mean absolute values and mean change from baseline values will also be presented graphically. Individual subject plots of expired CO levels will also be produced.

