The summary tables described above for number of cigarettes smoked daily and expired CO levels will also be produced for two subgroups of subjects, defined by smoking cessation status ('Ceased smoking', 'Continued smoking'). The graphs described above of mean absolute values and mean change from baseline will also be presented by smoking cessation subgroup.

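### Table 14.5.1.4 reports quit timing by dose only among Day 26 quitters, so a dose difference in timing is diluted and no all-subject quit-timing summary is planned (minor)

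*SAP*

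**What the plan says.** SAP 11.5.1 classes a subject as having ceased smoking if no cigarettes were smoked in the 24 hours before Day 26 and expired CO on Day 26 is below 10 ppm. Everyone else, including subjects with missing Day 26 data, is classed as continuing.

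Two sets of outputs are then built on that status:

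- **Quit day.** "For those subjects who had ceased smoking by Day 26, frequencies of the day of first smoking cessation" are presented by dose group and age group (Table 14.5.1.4, listed in SAP 14.5.1 as "Summary of First Day of Smoking Cessation for Subjects Who Ceased Smoking by Day 26"). First cessation means zero cigarettes, sustained without relapse.
- **Split tables.** The cigarette and CO summaries "will also be produced for two subgroups of subjects, defined by smoking cessation status" (Tables 14.5.1.3 and 14.5.1.6), with matching mean plots (Figures 14.5.1.3, 14.5.1.4, 14.5.1.7 and 14.5.1.8).

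Unsplit outputs by dose and age remain: cigarettes (Table 14.5.1.1), cessation status (14.5.1.2) and CO (14.5.1.5). SAP 10.1 sets a default that, unless otherwise specified, "the denominator for each percentage will be the number of non-missing observations". The table shells are redacted.

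On size, SAP 3.5 states: "A total of approximately 36 subjects will be randomised to the study, with approximately 18 subjects per treatment arm". SAP 3.6 stratifies by age "to ensure that each dose group has 6 elderly subjects and 12 non-elderly subjects". SAP 3.5 also states: "No specific hypothesis testing is planned".

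**The concern.** PD effect is a primary objective (SAP 2), and SAP 10.6 names the dose groups as the primary comparison of interest, so readers will compare the dose columns of any PD table. In Table 14.5.1.4 those columns contain only subjects selected by an outcome measured after 25 days of randomised dosing. If 3.0 mg makes more people quit, the additional quitters may be the harder cases, who quit late. They enter the 3.0 mg column and have no counterpart in the 1.5 mg column. The higher quit rate then shows up as little or no gain in timing.

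Nothing else in the plan summarises quit timing over all subjects, and nothing warns against a dose reading of the table. The split cigarette and CO tables have the same weakness, but there the all-subject results stand alongside.

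**Working it through.** **Plan's own figure.** The SAP gives no power, effect size or quit rate for PD. Only the allocation can be reproduced: 2 × (12 + 6) = 36, which agrees with SAP 3.5.

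**Assumptions.** All quit rates and effects below are assumed. The main model takes a constant daily hazard h of sustained quitting, with h = 0.015 (1.5 mg) and 0.030 (3.0 mg), and a range from 0.01/0.02 to 0.02/0.04.

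**1. All-subject percentage against quitter-only percentage.** The share of all subjects who have quit by day t is 1 − exp(−h·t). The share of Day 26 quitters who had quit by Day 12 is [1 − exp(−12h)] / [1 − exp(−26h)].

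| Hazards (1.5 / 3.0 mg) | All, by Day 12 | All, by Day 26 | Quitters only, by Day 12 |
|---|---|---|---|
| 0.01 / 0.02 | 11.3% v 21.3% | 22.9% v 40.5% | 49% v 53% |
| 0.015 / 0.030 | 16.5% v 30.2% | 32.3% v 54.2% | 51% v 56% |
| 0.02 / 0.04 | 21.3% v 38.1% | 40.5% v 64.7% | 53% v 59% |

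For the middle row: 0.1647/0.3229 = 0.510 and 0.3023/0.5416 = 0.558. The Day 12 gap falls from 13.8 points to 4.8. Across the rows the all-subject gap is about 10 to 17 points and the quitter-only gap about 3 to 6.

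**2. Can it reverse?** Take 18 subjects per arm: 6 would quit on either dose (Day 12 on 1.5 mg, Day 10 on 3.0 mg), 3 would quit only on 3.0 mg (Day 22), and 9 on neither. Nobody does worse on 3.0 mg.

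- Quitters only, mean quit day: 12.0 on 1.5 mg; (6×10 + 3×22)/9 = 14.0 on 3.0 mg. Of quitters, 6/6 = 100% v 6/9 = 67% had quit by Day 13. Both favour 1.5 mg.
- All subjects: 6/18 = 33% v 6/18 = 33% by Day 13, and 33% v 9/18 = 50% by Day 26. With non-quitters set to Day 26, mean days are (6×12 + 12×26)/18 = 21.3 v (6×10 + 3×22 + 9×26)/18 = 20.0. Nothing favours 1.5 mg.

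Varying the number who quit only on 3.0 mg from 0 to 4 moves the quitter-only difference (3.0 minus 1.5 mg) from −2.0 to +2.8 days, while the all-subject difference stays between −0.67 and −1.56. With none or one such subject there is no reversal.

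**3. How often, at 18 per arm?** A separate simulation of 20,000 trials used a latent propensity to quit:

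| Assumed effect | Quit day wrong sign: all subjects | Quit day wrong sign: quitters only | Reduction wrong sign: all subjects | Reduction wrong sign: continuers only |
|---|---|---|---|---|
| Moderate | 17% | 34% | 16% | 29% |
| Strong | 2% | 19% | 3% | 17% |

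The average conditioned difference kept the right sign in both scenarios. For quit day under the moderate effect it was −1.09 days among quitters and −1.65 over all subjects.

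**4. Cell size.** With 6 elderly subjects per dose, the chance of no quitter in a column is (1 − p)^6: 53%, 26%, 12% and 2% for assumed quit rates of 10%, 20%, 30% and 50%.

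**The case against.** The case on the other side is substantial.

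- **The effect is not hidden.** A reader might infer that the plan reports PD results only within cessation status and so conceals or reverses a dose effect. It does not: the split tables are additional, and Tables 14.5.1.1, 14.5.1.2 and 14.5.1.5 give cigarettes, quit rate and CO unsplit. This stands.
- **No formal inference is at risk.** SAP 10.1 carries a general rule, "All hypothesis testing will be carried out at the 5% (2-sided) significance level unless stated otherwise", but no PD test or dose contrast is planned; the PD outputs are descriptive. SAP 10.6 already calls the age-group analyses exploratory because of small numbers. This stands.
- **The denominator is not certain.** SAP 10.1 allows exceptions, the shells are redacted, and SAP 11.5.1 writes n and % for cessation status but only frequencies for quit day. The point on percentages is therefore conditional; the restriction to quitters is not.
- **The counts can be rebuilt.** Cumulating Table 14.5.1.4 over the column totals in Table 14.5.1.2 gives the all-subject percentages. True, but the SAP neither plans nor signals it.
- **Headline error rates mislead.** Under hazards 0.015/0.030, the quitter-only mean quit day points the wrong way in about 42% of simulated trials. The SAP plans frequencies, not that mean; its expected values (12.2 v 11.3 days) favour 3.0 mg; and no effect at all would give about 50%. Much of the figure is small-sample noise. The planned Day 26 quit rate points the wrong way in only about 5 to 9% across the hazards.
- **Day 26 values are only partly fixed.** It is tempting to say that all Day 26 rows in the split tables are set by definition. Only cigarettes in the ceased group are (zero); CO there is merely below 10 ppm, and values in the continuing group are free.

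**Conclusion.** The point holds, as a minor one. Table 14.5.1.4 compares doses within a group selected on an outcome of dose, and no all-subject quit-timing output is planned. Under the assumed hazards, a Day 12 gap of about 10 to 17 points over all subjects becomes about 3 to 6 points among quitters. Attenuation is the usual result. Reversal needs some subjects who quit late and only on the higher dose; it is possible, not inevitable.

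For Tables 14.5.1.3 and 14.5.1.6 and their figures, the risk is that a reader takes within-status columns as a dose comparison. The documents do not support the stronger inference that the report would miss or reverse a dose effect on cigarettes, CO or quit rate.

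The sizes rest wholly on assumed quit rates. The quitter-only percentages also assume that the redacted shell follows the SAP 10.1 default.

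**What to change.** 1. **Table 14.5.1.4.** Report cumulative n (%) of all PD Set subjects in each dose and age column who had begun sustained cessation by each day, or by Days 4, 13, 17, 21 and 26. Count subjects not confirmed as ceased at Day 26, including those with missing data, as not ceased. This matches the rule already in SAP 11.5.1. State the denominator in the table.
2. **Tables 14.5.1.3 and 14.5.1.6; Figures 14.5.1.3, 14.5.1.4, 14.5.1.7 and 14.5.1.8.** Add a footnote: cessation status is a post-randomisation outcome; dose columns within a status are not for dose comparison; ceased subjects have 0 cigarettes and CO below 10 ppm at Day 26 by definition. The layout by dose can stay.
3. **Dose statements.** Draw them from Tables 14.5.1.1, 14.5.1.2 and 14.5.1.5. Note that the PD Set is nested in the PK Set, which requires all doses on Days 1-3 and more than 90% on Days 4-25 (SAP 6.2 and 6.3). These tables are therefore also not a comparison of everyone randomised.

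The cost is one changed denominator, one footnote and a sentence of SAP text. No new data are needed.

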14.6 Other

14.6.1 Alcohol and Cotinine Results

Table 14.6.1.1	Summary of Baseline Urine Alcohol and Cotinine Results	Safety Set
Table 14.6.1.2	Summary of Prior Medications	Safety Set
Table 14.6.1.3	Summary of Concomitant Medications	Safety Set
Table 14.6.1.4	Summary of Extent of Exposure	Safety Set
Table 14.6.1.5	Summary of Duration of Exposure to Cytisine	Safety Set

Subject Data: Listings Contained in Report Appendix 16.2

16.2.1 Visit Dates, Dosing Information and Disposition

Listing 16.2.1.1	Visit Dates	Safety Set
Listing 16.2.1.2	Dose Administration	Safety Set
Listing 16.2.1.3	Drug Accountability	Safety Set
Listing 16.2.1.4	Subject Disposition	Safety Set
Listing 16.2.1.5	Additional Notes	Safety Set

16.2.2 Protocol Deviations

Listing 16.2.2.1	Protocol Deviations	Safety Set
------------------	---------------------	------------

16.2.3 Analysis Sets

Listing 16.2.3.1	Analysis Sets	Safety Set
------------------	---------------	------------

16.2.4 Demographic Data and Other Baseline Characteristics

Listing 16.2.4.1	Demographic Data	Safety Set
Listing 16.2.4.2	Medical History and Concurrent Conditions	Safety Set
Listing 16.2.4.3	Virology Result	Safety Set
Listing 16.2.4.4	Tobacco and Alcohol Use	Safety Set
Listing 16.2.4.5	Drugs of Abuse Results	Safety Set
Listing 16.2.4.6	Menstrual and Obstetric History	Safety Set
Listing 16.2.4.7	Pregnancy Test Results	Safety Set
Listing 16.2.4.8	Inclusion/Exclusion Criteria Failures	Safety Set
Listing 16.2.4.9	Eligibility Check	Safety Set

16.2.5 Drug Concentration Data and Pharmacokinetics

Listing 16.2.5.1	Plasma Cytisine Concentration Data	Safety Set
Listing 16.2.5.2	Urine Cytisine Concentration Data	Safety Set
Listing 16.2.5.3	Individual Derived Cytisine Pharmacokinetic Parameters	Safety Set
Figure 16.2.5.1	Individual Plasma Cytisine Concentration-Time Curves on a Linear Scale	Safety Set
Figure 16.2.5.2	Individual Plasma Cytisine Concentration-Time Curves on a Semi-Logarithmic Scale	Safety Set

